**Dependent variables:**

Neuropsychology:	Finger Tapping Task; Reaction Time Task (CANTAB); Trail Making Test, Part A; Digit Symbol Test; Effort Expenditure Rewards Task (EEfRT)
Self-report:	Snaith-Hamilton Pleasure Scale (SHAPS); Inventory of Depressive Symptoms-Self Report (IDS-SR); Beck Depression Inventory (BDI) Anhedonia Subscale; Multidimensional Fatigue Inventory (MFI); Profile of Mood States (POMS); State-Trait Anxiety Inventory (STAI) State Scale

**Objective 3: To determine whether peripheral and central cytokines and/or biomarkers of decreased dopamine synthesis predict connectivity and behavior before and after L-DOPA challenge.**

*Hypothesis 3:* Increased biomarkers of central and peripheral inflammation, and decreased cerebrospinal fluid (CSF) dopamine, its precursors and metabolites, will correlate with and predict greater fMRI and behavioral responses to L-DOPA

Patients described in Objectives 1 and 2 will undergo

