## 5. Study design and methods

Study Overview: Patients with major depression diagnosed based on DSM-V TR criteria between the ages of 18 and 65 (males, females and minorities) will be recruited to ensure a range of inflammation from low to high (as determined by plasma CRP). Research assessments will occur in the clinical research space of the Principal Investigator in the Emory Clinic Buildings and at the Emory University School of Medicine EUH CRN, a dedicated clinical research unit in the Emory University Hospital. Following a minimum of 2 screening visits to determine study eligibility (see inclusion and exclusion criteria below) and stability of plasma CRP concentrations (or at PI's, study physician or their designee's discretion), patients will undergo psychiatric assessments and ratings and will have a medical history and physical examination along with laboratory testing and research blood draw, and will undergo weight, height, waist circumference, body composition measurements, and a urine drug screen followed by behavioral testing. Patients may also be asked to undergo finger prick at screening or study visits to collect 20 ul of blood that will be used to rapidly measure CRP on a Diazyme hsCRP POC Test Kit (or equivalent as approved by PI or PI's designee) without patients having to undergo venipuncture. Patients may also be asked to have a lumbar puncture (LP) performed by an Emory Anesthesiologist on a separate visit between 7am-12 pm following hydration with 1 L of saline IV using standard sterile technique and local anesthesia with patients in the lateral decubitus position. Approximately 11 cc of CSF will be withdrawn. Upon completion of the LP, subjects will lie flat for approximately one hour and be subsequently discharged after ~4-6 hours from admission. Patients will participate in two additional outpatient study visits (see Table 1 for study protocol). The LP visit may occur approximately 1 week either before the first neuroimaging Study visit or one week after the last neuroimaging Study Visit, unless otherwise approved by the PI. After subjects have completed screening by meeting inclusion/exclusion criteria and moved into the L.P. and/or scanning visit phase of the study, an Abbreviated Clinical Interview and depression self-report (PHQ-9, see below) will be conducted if it has been more than 2 weeks since psychiatric assessments. Additional laboratory and medical assessments will be conducted if more than 4 weeks from screening, unless otherwise approved by the PI, study physician or PI's designee. This information will be used as study data and/or to improve patient safety by enabling monitoring of a subject's physical and psychiatric status during the study. Drastic fluctuations in psychiatric status (i.e. >25% change in depression scores) or medically significant changes in health status from H&P or labs will trigger a review by the Study Team (including the PI and/or study physicians) to evaluate appropriateness for continuation in the study and/or consider referral for further

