**Analytic Strategy, Objective 2:** Similar to the analytic strategy for Objective 1, post-L-DOPA or placebo administration neurocognitive performance or self-report scores will be entered into linear models with CRP (or other inflammatory markers) while controlling for pre-administration behavioral scores as well as relevant covariates. The difference (delta; post minus pre) in behavioral scores before and after placebo and L-DOPA will also be compared by paired T test, and between patients with high and low inflammation (CRP > or < 3mg/L). L-DOPA-related changes in functional connectivity in Objective 1 will then be compared to relevant post-LDOPA task-based and self-report behavioral responses using linear modeling.

**Analytic Strategy, Objective 3:** Relationships between functional connectivity and behavior before and after L-DOPA with central and peripheral inflammatory cytokines and their soluble receptors, and biomarkers of their potential effects on dopamine through decrease BH4 activity will be explored. Gene transcripts associated with inflammatory and metabolic signaling pathways related to inflammation effects on the brain have been used to predict response to pharmacological therapies (54, 95), including our previous work (96, 97). Therefore, genome-wide gene expression will be assayed. Plasma and CSF will be collected on a separate visit to measure IL-6, IL-1 $\beta$ , TNF and their soluble receptors, CSF BH4, dopamine, HVA and DOPAC, and plasma phenylalanine and tyrosine. Linear regression will be used to examine relationships between functional connectivity Z-scores or behavior (dependent variables) and biomarkers of inflammation and dopamine synthesis (independent variables), while controlling for covariates. Cytokines and their receptors will be examined first independently (with and without correction for multiple comparisons), then together in models to identify biomarker(s) that are most significant after backward and forward linear regression. If variables are collinear (as assessed by variance inflation factor, tolerance and leverage plots), principal component analysis (PCA) will be used.(98) Gene expression that correlates with CRP, or differs between patients with

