low versus moderate versus high CRP (<1, 1-3, and >3 mg/L) will be determined (5% FDR,  $p<0.05$ ). Gene lists will be analyzed for over representation of functional pathways and transcription factor binding regions per our previous work, (96, 97, 99) and correlated with connectivity Z-scores.

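### Objective 3 states a regression on connectivity and behaviour levels, so Hypothesis 3, that biomarkers predict response to L-DOPA, has no stated response analysis for the dopamine-synthesis markers or gene expression

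*Combined protocol and SAP*

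**What the plan says.** Section 4 words Objective 3 in two ways. Its heading asks whether biomarkers "predict connectivity and behavior before and after L-DOPA challenge", which is about levels. Hypothesis 3 beneath it is about response: raised inflammatory markers and low CSF dopamine, precursors and metabolites "will correlate with and predict greater fMRI and behavioral responses to L-DOPA".

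Section 7, Analytic Strategy, Objective 3, opens with "Relationships between functional connectivity and behavior before and after L-DOPA with central and peripheral inflammatory cytokines" and states one model: "Linear regression will be used to examine relationships between functional connectivity Z-scores or behavior (dependent variables", regressed on "biomarkers of inflammation and dopamine synthesis (independent variables), while controlling for covariates". Gene lists are likewise to be analysed for pathways "and correlated with connectivity Z-scores". Placebo is not mentioned in this part of Section 7. The covariate list at the end of Section 7 holds demographic and illness variables only; neither the pre-dose score nor the placebo-visit score is on it.

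On timing of the CSF sample, Section 5 says: "The LP visit may occur approximately 1 week either before the first neuroimaging Study visit or one week after the last neuroimaging Study Visit", unless the PI approves otherwise. The lumbar puncture is optional and the number expected is not given.

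**The concern.** A response to L-DOPA is a change attributable to the drug, and in this crossover the placebo visit identifies it. A regression of the post-L-DOPA score on a biomarker mixes two things: the marker's relation to the patient's usual level, and its relation to the drug effect. The protocol's own background reports lower corticostriatal connectivity in high-inflammation patients, so a biomarker–level association is expected before any drug is given.

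Two errors can follow. A marker of usual connectivity may be reported as predicting response. A marker that does predict response may be hidden, because the patients with the larger gain start lower. A separate, smaller matter is that CSF drawn after the dosing visits is not a prospective predictor, and the model does not record which samples those are.

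**Working it through.** **The plan's own power figure.** Section 7 gives dz about 1, n=30 per group, two-sided alpha 0.05, power above 80%. For a paired t test the noncentrality is 1 × √30 = 5.48 and power is 99.96% (99.9% at n=27). The statement is true as a lower bound, but it concerns the mean L-DOPA effect in high-inflammation patients. No power is given for Objective 3.

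**What Section 7 states for each objective.**

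| | Outcome | Pre-dose score used | Placebo used | Markers |
|---|---|---|---|---|
| Objective 1 | Post-dose Z scores; deltas | Yes | Yes | CRP; other inflammation measures if CRP fails |
| Objective 2 | Post-dose scores; deltas | Yes | Yes | CRP or other inflammatory markers |
| Objective 3 | Z-scores or behaviour | Not stated | Not stated | Cytokines, receptors, dopamine-synthesis markers; gene lists |

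Objective 1 uses one term for a level and another, delta, for a change. Read consistently, the Objective 3 outcome is a level.

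**Algebra.** Let x be a standardised biomarker, β its slope on usual connectivity (SD 1), γ its slope on the L-DOPA response, and σ the independent noise SD of each scan. The slope on x is then:

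- pre-dose level: β
- post-L-DOPA level: β + γ
- post-L-DOPA minus post-placebo: γ
- double difference (post minus pre, L-DOPA minus placebo): γ

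The level slope is non-zero when γ = 0 and β is not, and zero when γ = −β.

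**Illustration.** n=80 is the plan's analysis target. The slopes, σ = 0.7 (σ² = 0.49) and the absence of other between-patient variation in response are assumptions; the documents give none of them. With r = slope / outcome SD, the rejection rate is approximately Φ(|atanh r| × √(n−3) − 1.96).

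*Trait-only marker (γ = 0), post-L-DOPA level.* Variance is 1 + 0.49 = 1.49. At β = −0.3, r = −0.3/√1.49 = −0.246; 0.251 × √77 = 2.20; Φ(0.24) = 60%. At β = −0.2 and −0.4 the results are 31% and 85%. Simulation (20,000 replicates) gave 31%, 59% and 85%, with about 5% for each placebo-corrected outcome. Adjusting for the pre-dose score without placebo still gave 10%, 17% and 27%, because one scan is a noisy measure of usual level.

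*Exact full reversal (γ = −β).* At β = −0.3, γ = 0.3:

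- post-L-DOPA level: slope −0.3 + 0.3 = 0, so 5%
- double difference: r = 0.3/√(0.09 + 4 × 0.49) = 0.3/√2.05 = 0.210, so 46%
- post-dose difference: r = 0.3/√(0.09 + 2 × 0.49) = 0.3/√1.07 = 0.290, so 74% to 75%

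At 0.4 the three are 5%, 70% and 93%. Simulating the post-dose difference adjusted for the pre-dose difference gave 74% and 94%. In this model the adjustment neither helps nor harms; it would help if the two scans of a visit share visit-specific variation.

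*Less favourable cases for the placebo-corrected outcome.*

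- Half reversal (β = −0.3, γ = 0.15): level 20%, double difference 15%, post-dose difference 26%.
- Full reversal at 0.3 with n=40: post-dose difference 0.299 × √37 = 1.82, Φ(−0.14) = 44%.
- Full reversal at 0.3, n=80, with extra response SD of 0.5 or 1.0: r = 0.3/√1.32 or 0.3/√2.07, giving 65% or 46%.

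**The case against.** The level regressions are not a mistake in themselves: they match the Objective 3 heading, and Objective 3 is exploratory work in a pilot. That stands, and it confines the mismatch to Hypothesis 3.

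Objectives 1 and 2 already look at response. Objective 1 has a mixed model asking whether the L-DOPA effect depends on CRP, with other inflammation measures as a fallback; Objective 2 adjusts post-dose scores for pre-dose scores with CRP or other inflammatory markers. That stands too. A reader might infer that response goes untested for every biomarker, and the documents do not support this. What remains uncovered is BH4, dopamine, HVA, DOPAC, phenylalanine, tyrosine and gene expression.

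The plan looks before as well as after dosing. For a trait-only marker at β = −0.3 the pre-dose regression is significant in 59% of simulated trials, so a careful reader would often see that the association predates the drug. Under full reversal the association would be seen to disappear. This weakens any claim that a true predictor must be missed. But comparing one significant and one non-significant regression is not a test of change, and it leaves placebo out.

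A reader might also infer that late CSF samples are contaminated by L-DOPA. The documents show no such carry-over: a late lumbar puncture falls about a week after the last imaging visit, and one tablet is given at the L-DOPA visit. Only the order of events matters here, because a sample taken after the response cannot be described as having predicted it in advance.

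**Conclusion.** The point holds as an incomplete specification that should be corrected. As written, the Objective 3 regression estimates association with a level, and no analysis in the plan estimates how dopamine-synthesis markers or gene expression relate to the placebo-corrected response. The direction of the problem follows from the algebra alone. Its size does not: 31% to 85% significant for a trait-only marker, and about 5% power under full reversal, rest on assumed slopes, noise and n=80.

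Two stronger readings should be resisted. One is that the trial cannot test Hypothesis 3. The design can for connectivity, since resting-state scans are planned before and after dosing at both visits; the gap is in the stated analysis. The other is that a true predictor is cancelled out as a rule. Exact cancellation needs the response slope to equal the baseline slope with opposite sign, and the protocol's talk of reversal does not quantify that. At half reversal the placebo-corrected outcome itself has only about 26% power, so correcting the outcome makes the question the right one without making the analysis well powered.

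**What to change.** Revise Section 7, Analytic Strategy, Objective 3, including its gene-expression part.

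- **Connectivity response.** Make the outcome the L-DOPA-minus-placebo post-dose difference, adjusted for the pre-dose difference. Alternatively, fit a mixed model with an explicit biomarker-by-treatment (L-DOPA versus placebo) contrast. These are different models; state in advance which one is used.
- **Behavioural response.** Section 5 places self-reports in the morning and performance testing after the scans, so a same-visit pre-dose performance score, or a post-dose self-report, may not exist. Where there is no pre-dose score, use the L-DOPA-minus-placebo post-dose difference, and only for measures actually taken after dosing.
- **Level regressions.** Keep them, labelled as association with level rather than prediction of response.
- **CSF models.** Record whether the lumbar puncture came before or after the dosing visits, and describe only pre-dosing CSF as predicting response.

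The cost is analysis-plan wording; no new scans are needed. The price is precision: difference outcomes carry noise from two or four scans, and the CSF prediction analysis rests on the patients who agree to a lumbar puncture and have it before dosing, a number the documents do not give.

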**Dependent Variables:**

Neuroimaging and behavior: Functional connectivity and objective measures of behavior

Plasma and CSF Markers: IL-6, sIL-6R, TNF-alpha, sTNFR 2, IL-1 beta, IL-1ra, IL-10 and MCP-1; BH4, dopamine and dopamine metabolites, phenylalanine, tyrosine; mRNA expression of genes

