### **Analysis Plan and Statistical Methods:**

Descriptive statistics will be used to describe the central tendencies and variances of dependent variables and demographic and clinical characteristics of the patients. Due to the pilot nature of this project, we will use both targeted and exploratory data analysis methods to determine whether L-DOPA increases corticostriatal connectivity in depressed patient with high versus low inflammation. Statistical modeling will be conducted as described below. Log-transformation will be used for non-normally distributed data. Statistics will be two-tailed with alpha <0.05, and conducted in SAS and SPSS.

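### Objective 3 picks cytokine markers by forward and backward regression with no selection-adjusted test or validation, so noise alone would often yield a marker

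*Combined protocol and SAP*

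**What the plan says.** Section 7, Analytic Strategy, Objective 3 plans linear regressions with "functional connectivity Z-scores or behavior (dependent variables") on one side and inflammation and dopamine-synthesis markers on the other, adjusted for covariates. It then describes two steps for the inflammatory markers. First, "Cytokines and their receptors will be examined first independently (with and without correction for multiple comparisons"). Second, they are entered jointly, and the models are to single out the marker or markers that are "most significant after backward and forward linear regression". Principal component analysis is the fallback if variables are collinear.

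The general rule earlier in Section 7 is "Statistics will be two-tailed with alpha <0.05, and conducted in SAS and SPSS". No entry or stay threshold is given for the selection, and no correction method is named for the one-at-a-time step. For gene expression, in the same objective, associations with CRP "will be determined (5% FDR").

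The candidate list in Section 4, Objective 3 is "IL-6, sIL-6R, TNF-alpha, sTNFR 2, IL-1 beta, IL-1ra, IL-10 and MCP-1", in plasma and CSF. The list in Section 7 is shorter: IL-6, IL-1 beta, TNF and their soluble receptors.

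**The concern.** Forward and backward selection search many candidates and keep those with the smallest p-values. The p-values and R-squared of the final model are then computed as if that model had been fixed in advance. They take no account of the search, so they are too small and too large respectively. Nothing later in the Objective 3 plan corrects for this.

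At stake is whether a marker named under Objective 3 means anything. Hypothesis 3 in Section 4 is directional: it expects inflammatory and dopamine-pathway markers to predict the imaging and behavioural response to L-DOPA. If the selection usually returned nothing under the null, a returned marker would support that hypothesis. If it often returns something, the result says little.

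**Working it through.** **The plan's own figure.** The only power statement is for Objective 1 (Section 7, Power Analysis): dz about 1, n=30 per group, alpha 0.05, power above 80%. A noncentral t calculation for a paired test gives 0.9996 at n=30 and 0.9988 at n=27, so the bound holds. It has no bearing on this point. The plan gives no operating characteristic for Objective 3.

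**Inputs from the document**
- Two-sided alpha 0.05 (Section 7).
- 80 patients analysed (Section 5, Enrollment).
- Candidates k: about 6 (Section 7 list, 3 cytokines plus receptors), 8 (Section 4 list), or 8 × 2 = 16 if plasma and CSF are entered together.

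**Assumptions**
- Entry and stay p=0.05, because the plan states neither.
- Equal correlation between markers of 0 to 0.3.
- n=40 with CSF. Lumbar puncture is something patients may be asked to have, so the true number is unknown.
- Normal data, with covariates omitted.

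**Closed form.** For k independent null tests, P(at least one p<0.05) = 1 − 0.95^k:
- k=6: 1 − 0.735 = 26.5%
- k=8: 1 − 0.663 = 33.7%
- k=16: 1 − 0.440 = 56.0%

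**Simulation of the stated procedure.** The outcome is independent of every marker, and each cell has 600 to 1000 runs. The Monte Carlo standard error is at most √(0.5 × 0.5 / 600) = 2 percentage points. Entries are the chance of at least one selected marker for one outcome, over correlation 0 and 0.3:

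| n | k | Forward | Backward |
|---|---|---|---|
| 80 | 6 | 25-26% | 26-29% |
| 80 | 8 | 29-35% | 34-37% |
| 80 | 16 | 46-55% | 57-60% |
| 40 (assumed) | 8 | 33-36% | 38% |
| 40 (assumed) | 16 | 48-59% | 63-64% |

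A further run gave 25-31% (k=6), 33-39% (k=8) and 50-62% (k=16) at n=80, and 31-37% (k=8) and 49-63% (k=16) at n=40. The runs agree to within a few points. Forward selection alone, with correlated markers, falls up to about 4 points below those bands.

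**Apparent R-squared when a model is selected from noise.** This was about 0.08-0.10 at n=80 and 0.16-0.21 at n=40. With 16 markers another run reached 0.11 and 0.24. A floor follows by arithmetic. A single marker that just reaches p=0.05 has R² = t²/(t² + n − 2):
- n=80: 1.991² / (1.991² + 78) = 3.96 / 81.96 = 0.048
- n=40: 2.024² / (2.024² + 38) = 4.10 / 42.10 = 0.097

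**Sensitivity**
- With a stay level of 0.10, which the plan does not rule out, backward selection at n=80 gives 59-61% (k=8) and 84-85% (k=16).
- Over two independent outcomes at p=0.05, backward selection at n=80 gives 57-59% (k=8) and 82-84% (k=16).

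**Same null with a valid procedure**
- Benjamini-Hochberg at 5%: any hit in 4-6% of runs.
- Bonferroni over the k markers: 3.8-6.2%.
- Selection allowed only after a significant overall F test of the full marker model: 3.5-6.2%.

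**The case against.** The strongest reply is that this is the third objective of a self-described pilot. Section 7 says these relationships will be explored, and nothing here touches the primary connectivity outcome, the sample size or the conduct of the trial. That stands, and it limits the weight of the point. It does not make the selected p-values or R-squared correct. The plan also nowhere says that selected markers are hypothesis-generating or need confirmation.

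A second reply is that PCA will deal with related markers. It is conditional on collinearity and could shrink the pool, but it does not correct for selection.

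Several stronger readings are tempting, and the documents do not support them:
- A reader might count about 22 candidates by adding the six dopamine-pathway markers to the 16. The selection sentence has only cytokines and their receptors as its subject; the dopamine-pathway markers belong to the general regression plan. The defensible range is 6 to 16.
- A reader might infer that the cytokine panel has no multiplicity correction. Corrected one-at-a-time results are planned; the method is simply not named.
- A reader might infer that uncorrected results will be reported as findings. The plan says only that the markers will be examined both ways.
- A reader might infer that the selected cytokines are meant to steer later trials. Sections 2 and 3 give the foundation-for-future-studies role to corticostriatal connectivity as a brain biomarker.

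**Conclusion.** The concern holds for the multivariable selection step of Objective 3. Followed as written, with no true association and n=80, that step names at least one cytokine or receptor in about 25-31% (6 markers), 33-39% (8) or 50-62% (16) of single-outcome analyses. That is roughly 5 to 12 times the nominal 5% (25/5 = 5; 62/5 = 12.4). The model comes with an apparent R-squared of about 0.08-0.10. At an assumed n=40 with CSF, the figures are about 31-37% (8 markers) and 49-63% (16), with R-squared of about 0.16-0.21.

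The exact values depend on the assumed thresholds, marker correlation, number of candidates per model and CSF sample size, none of which the plan fixes. The conclusion does not change in any setting tried. It is worth correcting because the remedy is cheap, but it is confined to Objective 3.

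**What to change.** Amend Section 7, Analytic Strategy, Objective 3 as follows.

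1. Base marker claims on the one-at-a-time panel, judged at 5% FDR across all cytokines and receptors. This is the rule the plan already uses for gene expression. Show uncorrected p-values as descriptive only.
2. Replace forward and backward selection with one multivariable model that has a valid whole-model test. Two acceptable choices are a penalised model with cross-validated R-squared and a permutation p-value, or an overall F test of the full marker model that must be significant before any marker is named. Neither is the only right answer; the plan should fix one.
3. Keep PCA for collinear markers.
4. Label any marker named this way as hypothesis-generating.

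The cost is plan wording and modest programming, with no new data, visits or patients. The downside is fewer nominal hits, and some weak but real markers will not pass.

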
treatment. Additional CRP testing, psychiatric assessments, or medical assessments may be conducted as indicated by the PI, study physician or PI's designee. Prior to each MRI neuroimaging session, patients will undergo a urine toxicology screening (Testcup for drugs of abuse, or equivalent as approved by PI or PI's designee) for safety and exclusion of substance abuse. On the last screening visit, patients will undergo blood sampling in the morning (collected at the same time as blood draw for safety labs and/or CRP), and complete neurocognitive testing. During Study Visits 1 & 2, subjects will complete a series of self-reports in the morning, have MRI scans (including resting-state fMRI and ASL) pre- and post-L-DOPA or placebo administration from about 9 AM to 12:30 PM, and undergo blood sampling and selected neurocognitive testing after the MRI scans from about 12:30 to 2 PM. L-DOPA or placebo, which will be administered double-blind (randomized by the Emory IDS), will be administered in the waiting area of the Neuroimaging Facilities. Patient's vital signs will be monitored by a Study Physician or designated Nurse Practitioner before, during, and after drug administration. At each study visit, 6 ml of research blood will be collected at 4 degree for extraction of plasma to measure inflammatory markers and/or L-DOPA concentrations. Two 3 ml samples will be collected (at the screening visit #2 only) for whole blood mRNA gene expression. 2 buffy coat samples from the first research blood collected for plasma (screening visit #2) will also be stored for genetic analyses of relevant gene polymorphisms and DNA methylation. In order to further assess immune cell profiles, we will also collect 10 ml of whole blood in EDTA at room temperature for immune cell extraction. Some samples may be sent to other labs for additional analysis. Safety laboratory tests will be conducted at screening, which will include a hematocrit (CBC with automated differential), electrolyte panel (comprehensive metabolic panel), urinalysis with microscopic, and serum quantitative pregnancy test (for women only). A CRP test will be completed at both screening visits to establish stability, and may be repeated during study visits at the PI's or PI's designee's discretion. Subjects who smoke cigarettes must refrain from smoking 30 minutes before all blood draws and 2 hours prior to mRNA sampling. Subjects who smoke half a pack per day, or e-cigarette equivalent, will be offered a nicotine patch during study visits to reduce the effects of withdrawal on fMRI scans.

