from the study team upon first contact: "Please do NOT send any personal information via text. You may call the study team at [REDACTED] to discuss any personal or health details." Any PHI received via text message will be reported to the IRB as a potential breach of confidentiality.

Eligibility for completing further screening and baseline assessments: The PI or PI's designee will review information collected from the initial visit to determine whether subjects are eligible to proceed with further screening and collection of baseline assessments based on the following:

- (1) Attainment of informed consent
- (2) Psychiatric clinician has determined presence of current depressive symptoms at intake with QIDS score  $\geq 14$  or PHQ-9 score  $\geq 15$ , unless otherwise approved by the principal investigator or PI's designee
- (3) The patient has not informed study staff or the psychiatric clinician of any condition that, in the opinion of the PI or PI's designee, would make the patient unsuitable for or unable to complete further screening

Medical and data quality screening criteria for LP and randomization: Subjects determined to be eligible for the study will undergo a minimum of 2 screening visits. Subjects will be compensated \$50 at each screening visit. The screening visits will include the following assessments:

- (1) Structured Clinical Interview for DSM-V (SCID)
- (2) Mini Mental State Exam (MMSE), a standard, 27-item assessment of general cognitive functioning.
- (3) Childhood Trauma Questionnaire
- (4) Bipolarity Index
- (5) Scale for the Assessment of Negative Symptoms (SANS)
- (6) Salpêtrière Retardation Rating Scale (SRRS)
- (7) Wide Reading Achievement Test (WRAT-3)
- (8) Psychiatric History Form
- (9) HDRS
- (10) SHAPS-C
- (11) MGH-ATRQ (Lifetime and Current)
- (12) Medical history and physical exam performed by a physician or nurse practitioner.
- (13) CRP (This lab is collected at least twice to establish stability – the mean will be used for group assignment. A difference of greater than 50% between values or a CRP  $\geq 10$  mg/L will warrant additional CRP sampling.)
- (14) Laboratory testing including:
  - a) an electrocardiogram
  - b) complete blood count with automated differential
  - c) comprehensive metabolic panel (with renal and hepatic function tests)
  - d) antinuclear antibodies
  - e) glycosylated hemoglobin test
  - f) thyroid stimulating hormone
  - g) tests for HIV Ag/Ab, HBV Ag, and HCV Ab,

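### Objective 3 selects whole-blood genes by their association with CRP without accounting for leukocyte mix, so it cannot separate inflammatory signalling from cell proportions (minor)

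*Combined protocol and SAP*

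**What the plan says.** **RNA source.** Section 5 (Study Overview): "Two 3 ml samples will be collected (at the screening visit #2 only) for whole blood mRNA gene expression". This blood is not separated into cell types before the RNA is taken.

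**Selection.** Section 7, Analytic Strategy, Objective 3: "Therefore, genome-wide gene expression will be assayed". The selection sentence begins "Gene expression that correlates with CRP, or differs between patients with" and continues "low versus moderate versus high CRP (<1, 1-3, and >3 mg/L) will be determined (5% FDR", with p<0.05 also given. It names no covariate.

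**Use.** "Gene lists will be analyzed for over representation of functional pathways and transcription factor binding regions per our previous work". The lists are then correlated with connectivity Z-scores.

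**Purpose.** Baseline Assessments (Section 5) and Objective 3 (Section 7) both give inflammatory signalling as a reason for measuring expression. Objective 3 adds that such transcripts have served to predict response to drug treatment.

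**Covariates.** Objective 3 mentions control for covariates, but in the regression of connectivity or behaviour on biomarkers and not in the gene-by-CRP step. The covariate paragraph that closes Section 7 lists illness, treatment and lifestyle variables as optional and contains no leukocyte count.

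**Cell-count data.** The screening laboratory list includes "complete blood count with automated differential". Section 5 also plans a 10 ml sample for immune cell profiles, which is not linked to the expression analysis.

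**The concern.** A whole-blood expression value combines how strongly each cell type transcribes a gene with how many cells of that type are present. If the share of neutrophils, lymphocytes or monocytes moves with CRP, genes characteristic of those cells will move with CRP too, even if no cell has changed its transcription. False discovery rate control does not remove such genes, because their correlation with CRP in whole blood is real.

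What is at stake is interpretation. Enrichment on a list driven by cell mix could return immune-cell terms that look like inflammatory signalling, which is what the hypothesis leads one to expect, so the mistake would be hard to notice. The correlation of the lists with connectivity would inherit the same ambiguity.

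**Working it through.** The plan states no sample size, power or effect size for the gene-expression analysis, so it has no figure of its own to reproduce. The check has three parts.

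**1. Text.** The passages on RNA source, gene selection, covariates and cell counts were set side by side. None plans adjustment for cell composition, its estimation from the expression data, or a sensitivity analysis on it.

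**2. One gene.** Let r1 be the correlation of CRP with a leukocyte fraction, and r2 the correlation of a gene with that fraction. Suppose the gene has no relation to CRP once the fraction is fixed. Then

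- correlation of gene with CRP = r1 × r2
- correlation given the fraction = 0
- chance of p<0.05, two-sided = Φ(z − 1.96) + Φ(−z − 1.96), with z = atanh(r1 × r2) × √(n − 3)

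Inputs: n = 80 (Enrollment, Section 5; the plan does not say how many patients will have RNA) and two-sided alpha 0.05 (Section 7). r1 and r2 are assumptions, because the documents give neither.

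Example: r1 = 0.3, r2 = 0.7. The product is 0.21, atanh(0.21) = 0.213, √77 = 8.775, z = 1.870, and Φ(−0.090) + Φ(−3.83) = 0.464.

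| r1 | r2 = 0.5 | r2 = 0.7 | r2 = 0.9 |
|---|---|---|---|
| 0.2 | 14% | 24% | 36% |
| 0.3 | 26% | 46% | 68% |
| 0.4 | 43% | 71% | 91% |
| 0.5 | 61% | 89% | 99% |

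With the fraction as a covariate, each cell returns to about 5%.

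**3. Genome-wide, 5% false discovery rate.** Simulated studies with n = 80, 30% of genes tied to one leukocyte fraction, no direct CRP effect on any gene, and Benjamini-Hochberg selection.

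| Genes; studies | r2 | r1 | List non-empty | 10 or more genes |
|---|---|---|---|---|
| 8,000; 150 | 0.3 | 0.2 | 7% | 0% |
| 8,000; 150 | 0.5 | 0.1 | 11% | 1% |
| 8,000; 150 | 0.5 | 0.2 | 23% | 7% |
| 8,000; 150 | 0.5 | 0.3 | 43% | 23% |
| 8,000; 150 | 0.5 | 0.4 | 67% | 55% |
| 10,000; 100 | 0.7 | 0.2 | 21% | not tabulated |
| 10,000; 100 | 0.7 | 0.3 | 47% | not tabulated |
| 10,000; 100 | 0.7 | 0.4 | 82% | not tabulated |
| 10,000; 100 | 0.7 | 0.5 | 95% | not tabulated |

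A second run at r2 = 0.5 with 300 studies gave 18%, 44% and 73% for r1 = 0.2, 0.3 and 0.4. The simulation error near 50% is about √(0.25/150) = 4 points for 150 studies and √(0.25/100) = 5 points for 100.

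List sizes at r2 = 0.7, for r1 = 0.2, 0.3, 0.4 and 0.5: mean about 52, 390, 1,091 and 2,298; median 0, 0, 843 and 2,733. The median list was also empty at r2 = 0.5 with r1 = 0.2 or 0.3.

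With the fraction as a covariate, the list was non-empty in 3–6% of studies at r2 = 0.5 and in 1–5% at r2 = 0.7 (r1 from 0.2 to 0.5), with a mean below one gene. These runs adjust for the true fraction. A count from another day would adjust less completely.

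**The case against.** **Tier.** Section 7 describes a pilot with targeted and exploratory methods, and the Objective 3 relationships are to be explored. The primary outcome is connectivity Z-scores. No power statement or eligibility rule depends on the gene lists. This stands, and it sets the severity.

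**Estimand.** For a blood-based predictor of response, unadjusted whole-blood expression is a legitimate quantity. A shift in leukocyte mix can also be part of inflammation, so adjustment may remove a real pathway from CRP to expression. This stands too. A reader might infer that the unadjusted lists are false, or that the adjusted list should replace them. The documents support neither: the unadjusted association is a true whole-blood one, and the plan nowhere claims regulation within cells. What remains is that signalling is a stated purpose, and the unadjusted list alone cannot show it.

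**Size.** A reader might infer that the lists will be mostly artefact. That rests on assumed correlations, and the weaker assumptions give almost nothing. The plan also limits acute leukocyte shifts: infection and autoimmune disease are grounds for exclusion or rescheduling, and a CRP of 10 mg/L or more prompts resampling.

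**Data.** It is tempting to say that the needed covariate is already in hand for every RNA sample. The schedule table fixes safety laboratory tests at Screening #1 and has them only when indicated at Screening #2, whereas RNA is drawn at Screening #2. The two visits may fall on one day, and research blood accompanies safety tests and/or CRP, so a same-draw differential is possible but not assured.

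**Silence.** The covariate list is headed as demographic and illness-related, so it does not rule out laboratory covariates. The enrichment step refers to previous work, whose handling of cell mix cannot be seen here. By its title, one of the three cited studies concerns mononuclear cells, so its methods need not carry over to whole blood. Neither point amounts to a plan for cell mix.

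**Conclusion.** The concern holds as a limit on interpretation. As written, Objective 3 cannot distinguish genes whose transcription changes with CRP from genes that follow a change in leukocyte proportions, and it passes both into the pathway, transcription-factor and connectivity steps.

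The documents do not allow the size to be found. Under assumed correlations, and with no CRP effect within cells, it runs from negligible (list non-empty in 7% of studies, none with 10 or more genes) to substantial (non-empty in 95%, mean about 2,298 of 10,000 genes). These figures assume n = 80, 30% of genes tied to a single fraction, and the r1 and r2 values shown.

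Severity is minor. The analysis is exploratory and the primary outcome is untouched.

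**What to change.** In Section 7, Objective 3:

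- Keep the gene-by-CRP analysis as planned, unadjusted.
- Prespecify a companion model that adds neutrophil, lymphocyte and monocyte percentages from the differential count as covariates.
- Carry both lists through the pathway, transcription-factor and connectivity steps and report them side by side.
- Attribute a finding to signalling only where it persists after adjustment. Describe the rest as whole-blood associations that may reflect cell mix.
- Use the differential from the same draw as the RNA where there is one, otherwise the nearest screening differential, and state which was used.

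Settle this before expression results are seen. The cost is two or three extra covariates with about 80 patients and a second pass through the downstream steps. The adjusted list will omit CRP effects that act through cell numbers, which is why the unadjusted list stays.
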